#### EEG Measures.

For EEG recordings we will use 128 sintered Ag/AgCl active electrodes (ActiveTwo™ system, BioSemi B.V., Amsterdam). Electrodes will be placed according to equiradial layout on a head cap with snaps. Additional electrodes will be placed at reference locations of the mastoids, and around the eye to exclude data contaminated by eye blink artifacts. The analog-to-digital box receiving the electrode leads is battery-powered, so participants are electrically isolated and multiple safety mechanisms in the

ActiveTwo system limit current flow ([http://www.biosemi.com/faq/limit\\_current.htm](http://www.biosemi.com/faq/limit_current.htm)) takes about 30-45 minutes for two research staff members to apply the gel and snap on electrodes. EEG data will be acquired continuously, amplified, and digitized using Biosemi ActiveView software. Electrode placement reflecting head shape will be digitized using a Patriot™ Digitizer Stylus (Polhemus Co., Colchester VT) and Locator software (Source Signal Imaging, Inc., San Diego CA). The stylus touches each electrode site until registered by the software (5-10 minutes total). EEG recordings will high pass filtered (0.05 Hz), and low pass filtered (60 Hz, -12 dB/octave) to remove extraneous high and low frequency noise. EEG and EOG signals will be processed by voltage-controlled amplifiers and digitized for storage and analysis. Data will be processed offline based on data stored on computer workstation hard drives using BESA Research signal processing software.

1. The Auditory Oddball P300 Task (Donchin et al., 1978) is an event related potential (ERP) task known to be a valid index of attention and cognition. Subjects will attend to auditory stimuli. Using a classic oddball design, frequent tones will be jittered with rare tones for 1 block in a 3 to 1 ratio. Stimuli will be projected from computer speakers for 1500 ms. The sequence of blocks will be randomized and counterbalanced across subjects. A total of 320 auditory stimuli will be presented. The P300 is detected near the vertex of the scalp electrode array source localized to the right insula at a latency of 450 ms post stimulus. This task takes 15 minutes.
2. The Flanker Interference Task (Endrass et al., 2008; Eriksen and Eriksen, 1974) is an error monitoring task involving visual stimuli. A visual target stimulus is flanked by non-target stimuli that may either be congruent, incongruent, or neutral to the target response. Experimental stimuli will be displayed with Presentation software (Neurobehavioral Systems, San Francisco, CA) on an LCD monitor placed at a comfortable viewing angle. Trials begin with a fixation mark for 1100–1700 ms. 100 ms after onset of Flanker arrows, a central target arrow will appear for 30 ms. Subjects are to indicate the direction of the central target arrow with a button press. 500 trials will be presented, with 150 being compatible trials (with congruent flanker and target errors) and 350 being incompatible trials in pseudo-random order. To maintain time pressure and ensure an adequate number of error trials, subject response times will be recorded and subjects will be prompted to move more quickly based on a moving average of the past 50 correct trials. Error-related negativities (ERNs) will be recorded. This task takes 5 mins.

Timeline:

9:00	-30	Arrival, breath and urine tests
9:15	-15	Subjective and cardiovascular measures (baseline)
9:30	0	Capsule administration
10:00	+30	Standardized snack
10:30	+60	Subjective and cardiovascular measures
10:50	+80	Written self-report
11:00	+90	Subjective and cardiovascular measures, speech and behavioral tasks
11:30	+120	Subjective and cardiovascular measures
11:40	+130	Move to CNPRU and prepare EEG for recording
12:10	+160	EEG: auditory oddball P300 and Flanker task
12:30	+180	Subjective and cardiovascular measures
1:30	+240	Subjective and cardiovascular measures, 5D-ASC, SMS, End of Session Questionnaire

**Data Analyses:** The effects of the drug on subjective, behavioral, and cardiovascular measures will be assessed with mixed analysis of variance, with the between-subjects factor of group (adolescent, adult) and within-subjects factors of drug (placebo, 7.5 mg, 15 mg THC) and time (within session). Repeated measures ANOVA will compare ERPs including P300 amplitude between THC and placebo sessions.

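### At the stated trial timing, 500 Flanker trials need at least 10.25 min, not 5 min, so the EEG block as scheduled runs past the +180 min ratings

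*Combined protocol and SAP*

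**What the plan says.** The Flanker description under EEG Measures gives the trial count ("500 trials will be presented, with 150 being compatible trials", the other 350 being incompatible), the start of each trial ("Trials begin with a fixation mark for 1100–1700 ms"), and the stimulus: flankers lead by 100 ms, then "a central target arrow will appear for 30 ms". A button press follows, with no stated response window. Participants are prompted to speed up in order to "ensure an adequate number of error trials". The description ends: "This task takes 5 mins".

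The same section gives the auditory oddball task 15 min and 320 tones of 1500 ms. It puts electrode application at about 30 to 45 min and digitizing of electrode positions at 5 to 10 min.

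The Timeline has "Move to CNPRU and prepare EEG for recording" at +130, "EEG: auditory oddball P300 and Flanker task" at +160, and subjective and cardiovascular measures at +180. Drug Administration Sessions lists +180 as one of four post-dose times (60, 120, 180 and 240 min) for the ARCI, POMS, DEQ, heart rate and blood pressure. The Timeline also has a +90 row ("Subjective and cardiovascular measures, speech and behavioral tasks"). Participants return to the lab after the EEG measures. Under Participants, the group-by-drug interaction on DEQ Feel is the primary outcome. Under Data Analyses, time within session is an ANOVA factor.

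**The concern.** Five minutes for 500 trials leaves 0.6 s per trial, about half of the shortest fixation period alone. The count, the trial timing and the duration cannot all be right. The error also reaches the schedule, because the slot for the two EEG tasks is built on the 5-min figure and has no slack.

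If staff run all 500 trials, the participant is still in the EEG block when the +180 assessment is due. Nothing in the protocol says whether the ratings wait, interrupt a task or are taken in the EEG suite. Practice could then differ between a participant's three sessions, at a time point that feeds the primary measure and the time factor. If staff instead stop the Flanker at 5 min, fewer than half of the trials remain. That works against the protocol's own aim of collecting enough errors for the ERN, one of the two EEG outcomes it singles out.

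**Working it through.** **Inputs, all from EEG Measures and the Timeline.** 500 trials; fixation 1.1 to 1.7 s; flanker lead 0.10 s; target 0.03 s; Flanker stated at 5 min; oddball stated at 15 min; EEG tasks start at +160; ratings at +180. Response time is not given and is counted as zero. The 1.4 s midpoint fixation is an assumption.

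**The plan's own figure.** 15 + 5 = 20 min, and 180 − 160 = 20 min. The slot is reproduced exactly, so the Timeline uses the 5-min value. That value implies 300 s / 500 = 0.6 s per trial.

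**Flanker duration** = trials × (fixation + lead + target) / 60:
- fixation only, at its minimum: 500 × 1.10 / 60 = 9.17 min
- minimum: 500 × 1.23 / 60 = 10.25 min
- midpoint: 500 × 1.53 / 60 = 12.75 min
- maximum: 500 × 1.83 / 60 = 15.25 min

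**Trials that fit in 5 min:** 300 / 1.23 = 243 at minimum fixation, 300 / 1.53 = 196 at midpoint and 300 / 1.83 = 163 at maximum (rounded down).

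**End of the EEG block, set-up on time** = 160 + 15 + Flanker:
- minimum: +185.25
- midpoint: +187.75
- maximum: +190.25

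**Sensitivity to the oddball length.** Tone time alone is 320 × 1.5 / 60 = 8 min. The two tasks would then need 8 + 10.25 = 18.25 min at minimum fixation, 8 + 12.75 = 20.75 min at midpoint and 8 + 15.25 = 23.25 min at maximum, against a 20-min slot and before response time.

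**Set-up, as a note.** The slot is 160 − 130 = 30 min, for the move and preparation together. Electrodes take about 30 to 45 min; with digitizing the sum is 35 to 55 min. The protocol does not say whether digitizing comes before recording.

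**The case against.** The contradiction between 500 trials and 5 min has no good answer, since fixation alone exceeds 5 min. What can be contested is how much follows from it.

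- **The overrun depends on the 15-min oddball.** If that task took only its 8 min of tones, the block would fit at minimum fixation and miss by 0.75 min at midpoint, before response time. This stands as a caution on the size of the overrun. But 15 min is the protocol's own figure, and the Timeline slot matches it.
- **Set-up.** A reader might infer a second scheduling error from the 30-min slot. The documents do not support that. Thirty minutes lies within the stated approximate range of 30 to 45 min, and digitizing could follow recording. The slot has no slack, and no more than that can be said.
- **Cardiovascular readings.** The cuffs are portable, and Risk to subjects has a research assistant present throughout and monitoring heart rate and blood pressure. These readings can be taken in the EEG suite, so the concern is mainly the questionnaires.
- **Impact.** The shift is a matter of minutes at one of several post-dose times, nominally the same in every session and both groups. A reader might infer a biased group-by-drug test or a faulty sample size. Neither follows: no differential delay is shown, and the sample-size calculation does not use these durations.

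**Conclusion.** The concern holds as an internal contradiction that the session schedule relies on. The Flanker as described lasts at least 10.25 min, about twice the stated 5 min, and this floor needs no outside assumption. Taking the oddball at its stated 15 min and set-up on time, the EEG block ends roughly 5 to 10 min after the +180 assessment is due, before any response time. With set-up on time it still ends well before +240. The consequence is uncertain timing of the +180 questionnaires, or a shortened Flanker, with no rule to settle which. It should be corrected before sessions are run, but it does not call the primary comparison into question.

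**What to change.** 1. Reconcile the Flanker trial count, trial timing and duration. Either restate the duration as at least 10.25 min (about 13 min plus response time at midpoint fixation), or state a trial count that fits the slot. Correct the Timeline to match, with a realistic time for the move and EEG set-up.
2. State one way of taking the +180 ratings at +180 by the clock, the same in all three sessions, for example in the EEG suite at a fixed break between tasks. Choose it once the set-up time is settled.
3. Record actual minutes after the capsule for each rating and each EEG task.

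**Cost.** A Timeline change and, if 500 trials are kept, a longer EEG block. The examples below assume 10 min for the ratings (the gap the Timeline allows from +120 to +130), midpoint fixation, and 0 to 0.6 s of response time per trial, which adds 0 to 5 min.

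- *Break after the oddball.* Recording must start by 180 − 15 = +165, so move plus set-up may take at most 35 min. The Flanker runs from +190 to 190 + 12.75 = +202.75, or up to +207.75. About 32 to 37 min remain before +240.
- *Break before the oddball.* The oddball runs from +190 to +205 and the Flanker from +205 to +217.75, or up to +222.75. That crosses a +210 heart-rate and blood-pressure reading, if the 30-min interval under Cardiovascular Measures is counted from the capsule. It leaves about 17 to 22 min for return, cleanup and lunch, and moves both EEG tasks later relative to the expected peak effect named in Research Design.

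The alternative is fewer Flanker trials, and so fewer error trials for the ERN.

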## Protocol

Title: Age-Related Effects of THC (“Effects of drugs on behavior – ART” on the consent form)

Principal Investigator: [name], Ph.D.

Co-Investigators: [name]. and [name].

**Objectives:** **1)** To determine whether adolescents (defined here as ages 18-20) are at greater risk to acute oral 7.5 and 15 mg  $\Delta 9$ -tetrahydrocannabinol (THC) intoxication than adults (defined here as ages 30 to 40), **2)** to develop a sensitive behavioral measure to detect intoxication levels of THC, and **3)** to determine whether age-related drug effects are detectable using electroencephalography (EEG).

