**Background:** Increased accessibility to cannabis and its primary psychoactive constituent THC has raised public health concerns. One major concern surrounds the potential risks associated with acute THC intoxication and who might be most at risk. A second major concern is the need to develop sensitive measures that can detect THC intoxication after recent use and enable robust comparisons of intoxication to determine sources of risk. One potential source of risk is age, specifically during the period of adolescence. Preclinical studies indicate that adolescent rats are more sensitive to the acute effects of THC than adults (Cha et al., 2006; Quinn et al., 2008; Wiley et al., 2007), findings that are related to the brain during adolescence. Specifically, during this critical neurodevelopmental period, expression levels of the receptor that THC activates – the cannabinoid receptor (CB1R) – are more prevalent than any other period of life (Gee et al., 2016; Meyer et al., 2018). Due to this heightened expression of CB1R, the rodent brain is highly receptive to THC effects during adolescence (Heng et al., 2011). Similarly, in humans, CB1R expression peaks at ages 15-17 and declines to base levels near age 35 (Choi et al., 2012; Long et al., 2012), raising the possibility that adolescents are also at risk to heightened THC effects in humans. Notably, a recent report comparing responses to vaporized cannabis in adolescents vs adults indicated that adolescents reported *smaller* effects on certain subjective measures and less performance impairment. However, that study was complicated by possible differences in recent cannabis use and the fact that participants were not completely drug-free at the time of testing (Mokrysz et al., 2016). The purpose of the present study is to determine whether adolescence is a source of risk for THC intoxication in humans and to develop a new, sensitive behavioral assay to detect and compare THC effects. Greater sensitivity to acute THC intoxication may indicate higher potential for abuse, in addition to acute adverse effects including THC-induced psychosis and impairments in behavior and cognition.

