Our central hypotheses are 1) that the subjective, behavioral, and physiological responses to acute THC will be greater in adolescents, including reductions in EEG activity during task performance, and 2) that speech and text analyses will be sensitive indices of acute THC intoxication across dose and age. We and others have used analysis of speech production to detect effects of drugs, using measures of both production and content (Baggott et al., 2015; Bedi et al., 2014). To our knowledge, speech and text analyses have not been used to study THC. Our hypotheses will be tested using a well-established regimen of oral 7.5 and 15 mg THC administration in the laboratory (Childs et al., 2017; Pabon and de Wit, 2019; Wardle et al., 2015).

**Significance & Innovation:** Cannabis use is widespread among adolescents and young adults with over 11 million people ages 18-25 having consumed cannabis in the past year (2015) in the United States (National Institute on Drug Abuse). Furthermore, the average age of onset is 19 years of age (National Survey on Drug Use and Health). Cannabis products are increasingly accessible to young adults in the United States, a trend tied to increased use (Ter Bogt et al., 2014). For example, after cannabis was legalized in Colorado in 2011, past year cannabis use increased from 39% to 49% for ages 18-25 through 2017 (National Survey on Drug Use and Health). The consequences of long-term cannabis use are more severe in adolescents, and there is evidence that chronic use of cannabis in adolescents is associated with impaired neural maturation (Chadwick et al., 2013; Coffey and Patton, 2016). However, it is not established whether adolescents are more or less sensitive to the short-term effects of acute THC intoxication. Preclinical studies consistently show that adolescent rats are more sensitive to the acute effects of THC than adult animals (Cha et al., 2006; Quinn et al., 2008; Wiley et al., 2007). The period of sensitivity coincides with a neurodevelopmental period when cannabinoid receptors are most densely expressed in both rodent and human cortex (Choi et al., 2012; Gee et al., 2016; Heng et al., 2011; Long et al., 2012; Meyer et al., 2018). Therefore, human adolescents may also be more sensitive to the acute effects of THC, and under certain circumstances this may increase their risk for adverse effects such as psychosis and behavioral impairments, or likelihood of abuse.

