**Participants.** Participants will include 20 healthy male and female volunteers, half of whom will be aged 18-20 and the other half aged 30 to 40. The N of 20 participants is based on a reported effect size ( $f = 0.403$ ; Mokrysz et al., 2016) on our primary outcome measure (group x drug interaction on Drug Effects Questionnaire: "Feel"), which requires a sample size of 16 for at least 80% power at an alpha of 5% (G\*Power). The groups will be matched on number of males and females and on body mass index. Subjects will be excluded if they have a history of psychosis, nursing or pregnant, planning to become pregnant, or have a body mass index outside of 19 to 26. Subjects must have at least a high school education and fluency in English. Other criteria include individuals who have used the drug between 1 to 20 times lifetime and 0 times in last 30 days. Qualifying participants will agree to abstain from alcohol for 24 hours and other recreational drugs for at least 2 days before each session. They will be informed that breath and urine samples will be obtained on each session to verify abstinence. Participants will also be asked to fast 4 hours before the behavioral laboratory session.

**Drug.** THC (Marinol® [dronabinol]; Solvay Pharmaceuticals) will be orally administered in doses of 7.5 mg and 15 mg, in opaque capsules with dextrose filler. Placebo capsules contain only dextrose. The 15 mg dose reflects the amount of THC in one-half of a cannabis cigarette containing 0.2 g of 15% THC. These doses of THC are known to produce performance impairments as well as subjective intoxication (Broyd et al., 2016; Hartman and Huestis, 2013; Pabon and de Wit, 2019).

**Orientation Session.** During an initial, 30-min orientation session, study procedures will be explained and participants will read and sign a consent form. Participants will then practice the tasks and questionnaires that will be administered during the subsequent study sessions. A urine sample will be obtained to confirm abstinence from cannabis; subjects will be instructed to maintain abstinence from cannabis throughout the study and refrain from any use of drugs or alcohol for 24 before and 6 hours after each drug administration session. Participants will also be told to have a normal night's sleep and to fast 4 hours before the session; a standardized snack will be provided.

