Drug Administration Sessions. Three 5-hour drug administration sessions of placebo, 7.5 mg, or 15 mg Δ9-tetrahydrocannabinol (THC) will be separated by at least seven days. Each session will be conducted from 9 am to 1:30 pm in comfortably furnished study rooms that resemble living room settings. Upon arrival at the laboratory, participants will provide breath and urine samples to test for recent drug or alcohol use, and pregnancy (in females). Participants will complete the Addiction Research Center Inventory (ARCI) and Profile of Mood States (POMS) and provide measures for heart rate (HR) and Blood Pressure (BP) to assess their baseline state. Participants will consume a capsule containing 0, 7.5, or 15 mg THC under double-blind conditions. The order will be randomized across subjects. Participants will be provided a snack 30 min after administration. Participants will complete the ARCI, POMS, and Drug Effects Questionnaire (DEQ) 60, 120, 180, and 240 min after taking the capsule; heart rate (HR) and Blood Pressure (BP) will be taken at the same time. During peak drug effects, participants will complete a 10-min written self-report, 5-min monologue speech task and several behavioral tasks, including the Stop Task, N-Back Task, and Time Production Task (TPT) in randomized order. At 130 min post-administration, participants will be accompanied across the hall to the EEG center for two tasks: the Auditory Oddball P300 and Flanker Interference task. After EEG measures, participants will return to the lab and subjects will be given lunch. At 240 min subjects will complete the 5 Dimensions of Altered States of Consciousness (5D-ASC) scale, the State Mindfulness Scale (SMS) and an End of Session Questionnaire before being discharged. In the interest of safety, for subjects who cannot arrange a ride home, we will pay for transportation home. After the final session, participants will be informed of the purpose of the study including the drug that they received and will be allowed to ask any additional questions about the study.

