- 2. The Profile of Mood States (POMS; McNair et al., 1971) is a 72-item questionnaire used to assess momentary mood states across 8 subscales: Anxiety, Depression, Anger, Vigor, Fatigue, Confusion, Friendliness, and Elation. Participants will indicate how they feel at that moment in relation to 72 adjectives on a 5-point scale from "Not at all" (0) to "Extremely" (4).
- 3. The Drug Effects Questionnaire (DEQ; Morean et al., 2013) is comprised of 100 mm visual analog scales (VAS) to provide ratings to five questions: "Do you feel any drug effect?" ("None at all" to "A lot"); "Do you like the effects that you are feeling now?" ("None at all" to "A lot"); "Do you dislike the effects that you are feeling now?" ("None at all" to "A lot"); "Are you high?" ("Not at all" to "Very"); and "Would you like more of what you consumed, right now?" ("Not at all" to "Very much"). The measure of primary interest is the "feel" question.
- 4. The 5 Dimensions of Altered States of Consciousness (5D-ASC; Studerus et al., 2010) scale consists of 94 statements describing common features of altered states of consciousness (ASC), independent of their means of induction. In developing the scale, 11 ASC induction mechanisms including THC were used. The 5D-ASC contains five dimensions of ASC: Oceanic Boundlessness, Dread of Ego Dissolution, Visionary Restructuralization, Acoustic Alterations, and Vigilance Reduction (Studerus et al., 2010). Subjects respond to statements on a 100 mm visual analog scale indicating how they feel relative to their normal waking consciousness and the degree to which they experienced each item during that day's session. The 5D-ASC is often used in studies of 'classical psychedelics' which bind 5HT-2A serotonin receptors. Although THC was included in the development of this scale, we note that measures of THC effects will

be exploratory. We know of no previous THC studies that have incorporated the 5D-ASC. The 5D-ASC will be administered once at the end of each session.

5. The State Mindfulness Scale (SMS; Tanay and Bernstein, 2013) is comprised of two subscales, including a 15-item mindfulness-of-mind subscale and six-item mindfulness-of-body subscale (sample item: "I clearly physically felt what was going on in my body"). With each item, participants provide ratings on a five-point scale from "Not at all" to "Very much." The SMS will be administered once at the end of each session.

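### Data Analyses gives no rule for incomplete sessions, and the planned ANOVA in its usual form drops a participant from every outcome with a missing cell; a mixed model would keep the observed data

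*Combined protocol and SAP*

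**What the plan says.** Data Analyses states that "The effects of the drug on subjective, behavioral, and cardiovascular measures will be assessed with mixed analysis of variance". Age group is the between-participant factor; drug (placebo, 7.5 mg, 15 mg) and time within session are the within-participant factors. The next sentence plans a repeated-measures ANOVA comparing ERPs between THC and placebo sessions. The document gives no rule for a session that is missed, cut short or lacking a rating, and it states no expected dropout rate.

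The Participants section names the primary outcome as the "group x drug interaction on Drug Effects Questionnaire", on the Feel item. It gives 16 as the required sample size and plans 20, which is 10 per age group. It does not call the extra four a dropout allowance.

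Drug Administration Sessions schedules the "Drug Effects Questionnaire (DEQ) 60, 120, 180, and 240 min after taking the capsule", in each of three sessions. The Timeline also lists subjective measures at +90 minutes without naming the instruments. It places the written self-report at +80, speech and behavioral tasks at +90, the EEG tasks at +160, and the 5D-ASC, State Mindfulness Scale and End of Session Questionnaire at +240.

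**The concern.** Classical mixed ANOVA works on a complete set of drug-by-time cells for each participant. Unless the plan says otherwise, standard practice is to delete a participant with any missing cell from that outcome's analysis. Valid ratings are then thrown away in a trial with 10 people per age group.

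A second consequence is possible. Objective 1 asks whether adolescents "are at greater risk to acute oral 7.5 and 15 mg" THC than adults. If sessions were stopped because of strong reactions, deletion would remove the people with the largest drug effects. If that happened more in one age group, the estimated age difference would move.

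**Working it through.** **The plan's sample size.** Inputs from Participants: f = 0.403, alpha 5%, power at least 80%, two groups. The number of measurements m and their correlation ρ are not given, so they are assumptions. For the within-between interaction, λ = f² × N × m / (1 − ρ), with df (m − 1) and (N − 2)(m − 1).
- m = 2, ρ = 0.5, N = 16: λ = 0.1624 × 16 × 2 / 0.5 = 10.39, power 0.850. N = 14 gives 0.790, so 16 is the smallest even N.
- m = 3, ρ = 0.3, N = 16: λ = 0.1624 × 16 × 3 / 0.7 = 11.14, power 0.815. This also gives 16.

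The stated 16 is therefore reproduced. Under these two settings power is 0.926 or 0.903 at N = 20, 0.894 or 0.865 at N = 18, and 0.790 or 0.749 at N = 14. The formula assumes equal groups.

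**What deletion discards.** DEQ ratings per participant: 4 times × 3 sessions = 12, or 5 × 3 = 15 if the DEQ is also given at +90.
- One session stopped after 120 minutes: 2 ratings missing, 10 of 12 (or 13 of 15) observed, none used for Feel.
- Withdrawal after two sessions: 8 of 12 (or 10 of 15) observed, none used.
- By the Timeline, the written report (+80) and the speech and behavioral tasks (+90) are already complete at a 120-minute stop and stay in their own analyses. That session's EEG (+160) is lost.

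**Precision.** The standard error of a difference between group means is proportional to √(1/n₁ + 1/n₂).
- One of 10 lost: √[(1/9 + 1/10) / (2/10)] = 1.027, an increase of 2.7%.
- Two of 10 lost: √[(1/8 + 1/10) / (2/10)] = 1.061, an increase of 6.1%.
- Error df for group by drug, (N − 2) × 2: 36 at N = 20, 34 at 19, 32 at 18.

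**How many might be lost.** No rate is stated. If a share p of sessions is incomplete, independently, the share of participants deleted is 1 − (1 − p)³. For p = 2%, 5% and 10% this is 6%, 14% and 27%, leaving about 18.8, 17.1 and 14.6 of 20.

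**Bias, as an illustration.** Assumptions: 10 per group, total rating SD about 1, true age difference 0.5 at 15 mg, participant SD 0.5, and session and residual SDs of 0.7 and 0.5 or the reverse. The strongest 15 mg reactor or reactors in one age group lose all ratings after 120 minutes. There were 400 simulated trials per setting, with four or five rating times. The table gives the shift, against full data, in the adolescent-minus-adult difference in 15 mg minus placebo.

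| Loss | ANOVA with deletion | Mixed model, all ratings kept |
|---|---|---|
| One adolescent, loss follows the 120-min rating | −0.061 to −0.098 | within 0.001 |
| Two adolescents, same | −0.104 to −0.177 | within 0.003 |
| One adolescent, loss follows later unseen ratings | −0.068 to −0.106 | −0.015 to −0.037 |
| Two adolescents, same | −0.121 to −0.187 | −0.027 to −0.072 |
| One adult, loss follows the 120-min rating (four times) | +0.070 to +0.096 | within 0.003 |

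The sampling SD of the estimate is 0.36 to 0.49. When one strongest reactor is lost from each group, the deletion shift is 0.00. The mixed model fitted here has the structure that generated the data, so its column is a best case.

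**The case against.** The strongest reply is that the problem is hypothetical and small. No document predicts early stops, a completion bonus of $100 encourages attendance, and 20 participants exceed the stated 16. At N = 18, power is still 0.865 to 0.894 under the settings that reproduce the plan's figure. The bias illustration is adverse by construction, because it removes the strongest reactors from one age group only. All of this stands, and it limits the severity. It does not remove the gap: the plan has no rule, and the alternative costs little.

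A reader might infer three stronger claims that the documents do not support.
- *An incomplete session removes the participant from the whole study.* It does not. Deletion is per outcome, and tasks finished before the stop survive.
- *The age comparison will be biased.* That needs reaction-driven losses that differ by age, and nothing in the documents shows either.
- *The trial must add a symptom checklist because nausea, dizziness and loss of balance are not recorded by age.* The risk section lists these effects and no described measure names them. But participants complete "an End of Session Questionnaire before being discharged" whose items are not shown, the written report invites any sensations, and the DEQ has a dislike item. The harms named in the rationale ("this may increase their risk for adverse effects such as psychosis and behavioral impairments, or likelihood of abuse") are at least partly measured. With 10 per group a by-age table would also be descriptive only: 5/10 against 0/10 is needed for two-sided Fisher p < 0.05 (p = 0.033), and 4/10 against 0/10 gives p = 0.087.

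**Conclusion.** The point holds as a missing-data gap with a better method available. It is not a flaw shown to change the primary conclusion. For one or two losses in one age group the cost is a 2.7% to 6.1% larger standard error and the loss of valid ratings. In the adverse illustration the bias is 0.06 to 0.11 SD for one loss and 0.10 to 0.19 SD for two, well inside the sampling SD. These bias figures rest on assumed variances and an assumed loss pattern. The conclusion also assumes that the ANOVA is run in its usual complete-cell form, since the plan names neither software nor a missing-data method. Severity: minor to moderate.

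**What to change.** Replace the two ANOVA sentences in Data Analyses with text along these lines:

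> Subjective, behavioral and cardiovascular measures will be analysed with a linear mixed model fitted by REML, with fixed effects of group, drug, time (where repeated within session) and their interactions, and a random participant effect. Measures repeated within session will also have a random participant-by-session effect. Kenward-Roger degrees of freedom will be used. All observed values will be included. ERP outcomes will be analysed in the same way with group, drug and a random participant effect. The number of incomplete sessions and withdrawals will be reported by dose and age group, with reasons.

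With complete data and the same covariance structure, this gives essentially the ANOVA result for group by drug. The small-sample correction matters in the replacement model. An uncorrected chi-square test of group by drug would have a type I error of P(F(2, 36) > 5.991/2) = 6.3%; the planned ANOVA F test does not have this defect. In the ERP model, a participant who misses one EEG session keeps the others, and including group serves objective 3.

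The costs are a little more analysis work and a covariance structure that must be fixed in advance. Repair is only partial if loss depends on later effects that were not observed: in the illustration 15% to 58% of the deletion shift remained. A session that ends before the 60-minute rating still contributes nothing to the DEQ analysis, but that participant's other sessions are kept.

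An optional clarification: if the End of Session Questionnaire asks about nausea, dizziness and balance, say so, and give it at early stops as well.
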